6.1.2 Medical History

Medical/surgical history data will be coded using the Medical Dictionary for Regulatory Activities (MedDRA) version 24.0. It will be summarized and presented using system organ class (SOC) and preferred term (PT). The SOC will be presented in alphabetical order and the PT will be presented in alphabetical order within each SOC. The number and percentage of subjects with a particular condition/diagnosis will be summarized overall and by weight group (≤ 40 , > 40 kg) based on the Safety population. Subjects reporting more than one condition/diagnosis within a body system will be counted only once for that body system.

6.1.3 Prior and Concomitant Medications

Prior and concomitant medications will be recorded and coded using the Anatomical-Therapeutic-Chemical (ATC) classification text from the World Health Organization Drug Dictionary (WHO-DD) version, March 1, 2021. They will be summarized overall and by weight group (≤ 40 , > 40 kg) based on the Safety population. A prior medication is defined as any medication taken prior to the first dose of study drug. A concomitant medication is defined as any medication that started prior to the first dose of study drug and continued to be taken after the first dose of study drug or any medication that started after the first dose of study drug, but not after the last dose of study drug. Medications with unknown or incomplete end date will be considered concomitant unless there is clear evidence that the medication was stopped prior to the first dose of study drug. The number and percentage of subjects who have taken medications will be summarized by ATC Class 3 and generic drug name, separately for prior and concomitant medications.

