8.4 Prior and Concomitant Therapy

Any prior, concomitant, or procedural medications or therapy given to or taken by the subject within 24 hours before and up to the end of the observation period (3 days post OPTISON

administration) will be recorded in the CRF along with the indication. Either the generic or the trade name may be recorded. The sponsor will encode all therapy and medication according to a current well-recognized dictionary of medical codes.

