9.4 Post-Treatment Period

After completion of contrast administration and imaging acquisition, the subjects will be monitored at the following time points for safety assessment:

- At 10 ± 5 minutes and 30 ± 5 minutes after the last OPTISON administration, 12-lead ECG will be recorded. Investigators may also record 12-lead ECG at additional time points if thought to be clinically relevant; however, only 12-lead ECG recordings at 10 ± 5 minutes and 30 ± 5 minutes will be considered as study data.
- At 10 ± 5 minutes and 1 hour ± 5 minutes after the last OPTISON administration, vital signs and pulse oximetry will be obtained.
- A physical examination will be performed at 1 hour ± 5 minutes. The occurrence of AEs and SAEs will be monitored and recorded.
- At 24 ± 4 hours and 72 ± 8 hours after the last OPTISON administration, the subject's parents or legal guardian will be contacted by telephone for assessing AEs/SAEs and recording concomitant medications.
- The subject's parent/guardian will be provided with an emergency phone number and instructed to contact study site personnel with any questions or concerns. The subject's parent/guardian may be called at any time if considered necessary by study personnel.

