10.3.5 Adverse Events

The AE profile of OPTISON has not yet been established in pediatric patients. Study personnel must remain vigilant for the occurrence of AEs, particularly those that may be life threatening. Personnel who are trained in the management of acute anaphylaxis and other emergencies and who have access to appropriate clinical supplies must be immediately available for at least 30 minutes to observe for possible anaphylactoid reactions after dosing. Treatment of SAEs should be primarily supportive of vital functions.

An AE is defined as any untoward medical occurrence in a patient or clinical investigation subject which does not necessarily have to have a causal relationship with the study treatment. AEs will be asked for from time of informed consent through 72 ±8 hours after the last administration of contrast agent.

A TEAE is any unfavorable and unintended sign, symptom, or disease temporally associated with the use of OPTISON, whether or not considered related to that product. Only symptoms/signs that begin or worsen in severity and/or frequency after OPTISON administration/use will be recorded as TEAEs in the CRF.

The subjects will be closely observed and questioned for any kind of AE during the study procedures and at follow-up appointments throughout the study period with non-leading questioning (e.g., "How do you feel?"). The subjects will be instructed to immediately report any symptoms and signs to the study staff (i.e., between formal observations).

See section [10.3.8](#) for documentation of SAEs in the CRF.

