1. Evaluation of Left ventricular (LV) Endocardial Border Delineation (EBD)
2. Evaluation of diagnostic confidence for the assessment of LV EBD and wall motion
3. Evaluation of Left Ventricular Opacification (LVO)
4. Evaluation of Image Quality and Diagnostic Usefulness
5. Evaluation of Left Ventricular Function
6. Evaluation of diagnostic confidence for the assessment of LVEF
7. Evaluation of Duration of Contrast Enhancement.

Clinical safety data will be collected throughout the study, beginning from dosing through 72 hours post OPTISON administration to determine the safety profile of intravenous administration of OPTISON at various doses in pediatric population.

Figure 1 Study Diagram

All efficacy and safety measurements obtained during the course of the study are summarized in the Study Schedule of Events ([Table 2](#)).

Table 2 Study Schedule of Events

Variables	Pre-procedure		Dosing/ Imaging (0)	Post-last OPTISON Administration				
	Screening (≤2 weeks)	Baseline (from -1 ± 1 h)		10 min (±5 min)	30 min (±5 min)	1 h (±5 min)	24 h (±4 h)	72 h (±8 h)
Informed Consent	X							
Entry Criteria	< ----- >							
Demographic Information	X							
Medical/Surgical History	X							
Pregnancy test ^a	X	X						
Physical Examination		X				X		
Vital Signs		X		X		X		
SaO ₂ by Pulse Oximetry		X	X	X		X		
12-Lead ECG Recording		X		X	X			
Prior and concomitant Medications ^b		< ----- >						
Continuous ECG Monitoring ^c			< ----- >					
OPTISON Administration			X					
Image Acquisition		X	X					
Phone Calls							X	X
AEs and SAEs Monitoring	X	<----->						

AE = Adverse event; ECG = Electrocardiogram; SAE = Serious adverse event; SaO₂ = Oxygen saturation

a Urine β-hCG pregnancy test at screening and at pre-dose; post-menarchal females only.

b Any prior or concomitant medication taken by the subject within 24 hours before OPTISON injection and up to the end of the 72-hour follow-up period.

c Continuous ECG monitoring is from time of first OPTISON injection until 30 minutes after the last OPTISON injection

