6.5.2 Analysis of Adverse Events

6.5.2.1 Treatment-Emergent Adverse Events

An AE will be considered as treatment-emergent if it starts or worsens after OPTISON administration. Any AE with an onset on the day of IMP administration for which the time of onset is missing will be assumed to be treatment-emergent.

All summaries of AEs will be based on TEAEs and will be prepared by weight group (≤ 40 , > 40 kg) and overall for the Safety Population. AEs will be mapped to System Organ Class (SOC) and preferred terms using the MedDRA version 24.0. All AEs will be listed.

An overall summary of TEAEs will present the number (%) of subjects and number of events for the following events:

- TEAE
- Severe TEAE
- Serious TEAE
- TEAE considered related to IMP
- Serious TEAE considered related to IMP
- TEAE leading to discontinuation of study drug
- TEAE leading to death

The number and percentage of subjects experiencing TEAEs, and the number of events will be summarized by SOC and preferred term in alphabetical order. Summaries of TEAEs by maximum severity and TEAEs considered related to the study drug will also be presented by SOC and preferred terms.

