14.3.2.4	Summary of Treatment Emergent Adverse Events Leading to Study drug Discontinuation by System Organ Class and Preferred Term	Safety
14.3.3.1	Summary and Change from Baseline – Vital Signs	Safety
14.3.3.2	Shifts from Baseline to Post-Administration Timepoints – Vital Signs	Safety
14.3.4.1	Summary and Change from Baseline – Electrocardiograms	Safety
14.3.4.2	Shifts from Baseline to Post-Administration Timepoints – Electrocardiograms	Safety
14.3.4.3	Summary of Overall Interpretation by Timepoint - Electrocardiograms	Safety
14.3.4.4	Shift from Baseline to Post-Administration Timepoints of Overall Interpretation - Electrocardiograms	Safety
14.3.4.5	Summary of QTc Interval Outlier Categories	Safety
14.3.5	Shift from Baseline to Post-Administration Timepoint – Physical Examination	Safety

LISTING NUMBER	LISTING TITLE	POPULATION FOR ANALYSIS
16.2.1	Subject Disposition	All Subjects
16.2.2	Protocol Deviations	All Subjects
16.2.3	Inclusion/Exclusion Criterion	All Subjects
16.2.4.1	Demographic Information	Safety
16.2.4.2	Medical History	Safety
16.2.4.3	Prior and Concomitant Medications	Safety
16.2.5	Exposure to OPTISON	Safety
16.2.6.1	Visualization of Segments	ITT
16.2.6.2	BIE Interpretations	ITT
16.2.6.3	Non-Contrast and Contrast Enhanced Comparisons	ITT
16.2.6.4	Dose Suitability	ITT
16.2.7.1	Adverse Events	Safety
16.2.7.2	Deaths	Safety
16.2.7.3	Serious Adverse Events	Safety
16.2.7.4	TEAEs leading to discontinuation of study treatment	Safety
16.2.8.1	Vital Signs	Safety
16.2.8.2	Electrocardiogram – Reader Results	Safety
16.2.8.3	Electrocardiogram – Overall Interpretation	Safety
16.2.8.4	Physical Examination	Safety

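### SAP 6.1.3 drops a fully dated medication started after the last injection from both medication tables, although medications are collected for 72 hours

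*SAP*

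**What the plan says.** SAP 6.1.3 defines two categories. A prior medication is one taken before the first dose. A concomitant medication is one that began before the first dose and continued after it, or "any medication that started after the first dose of study drug, but not after the last dose of study drug". The section then adds a default for poorly dated records: "Medications with unknown or incomplete end date will be considered concomitant unless there is clear evidence" that the drug stopped before the first dose. SAP Section 8 plans one table for each category, 14.1.4.1 (prior) and 14.1.4.2 (concomitant), both on the Safety population. There is no third category or table.

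Collection runs much longer than dosing. Protocol 8.4 records medications taken "within 24 hours before and up to the end of the observation period", which it sets at 3 days after OPTISON. Footnote b of SAP Table 2 gives the same window: "within 24 hours before OPTISON injection and up to the end of the 72-hour follow-up period". Under Protocol 9.4, at 24 and 72 hours after the last administration the parent or guardian is "contacted by telephone for assessing AEs/SAEs and recording concomitant medications".

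The adverse event rule in SAP 6.5.2.1 has no such cut-off: "An AE will be considered as treatment-emergent if it starts or worsens after OPTISON administration".

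**The concern.** OPTISON is given as a few boluses in one session, so nearly all of the post-dose collection period comes after the last injection. A definition of concomitant use that stops at the last dose suits a drug taken over weeks. Here it excludes the period in which treatment of a reaction is most likely to be recorded. Protocol 10.3.5 requires trained staff who "must be immediately available for at least 30 minutes to observe for possible anaphylactoid reactions after dosing". A single, fully documented drug given in that period for a reaction to the last injection would not be tabulated, while the reaction itself would be counted as treatment-emergent.

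The rule also works backwards on data quality. Taken literally, better documentation of the end date removes a record from the table.

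At stake is the accuracy of Table 14.1.4.2 as a summary of medication use after dosing, in a study with pediatric safety as a secondary objective.

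**Working it through.** The plan states no figure to reproduce. The check applies the SAP 6.1.3 definitions as rules, with the first dose at time 0 and the last dose at time L.

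**Step 1: classification of five medication patterns**

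| Pattern | Prior (14.1.4.1) | Concomitant (14.1.4.2) |
|---|---|---|
| Stopped before the first dose | yes | no |
| Started before the first dose, continued after it | yes | yes |
| Started between first and last dose | no | yes |
| Started after the last dose, complete end date | **no** | **no** |
| Started after the last dose, incomplete end date | no | yes |

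The last two rows can be the same drug given at the same moment, for example 15 minutes after the last injection. They differ only in whether the end date is complete.

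**Step 2: how much of the collection period is affected**

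SAP Table 2 has five scheduled post-dose time points (10 min, 30 min, 1 h, 24 h, 72 h), all timed from the last administration. A new, fully dated drug started at or after any of them is in 0 of 2 tables.

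As a share of time, a new start counts as concomitant for L / (L + 72 h) of the window after the first dose:

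- L = 10 min (the minimum gap between dose levels, SAP 2.2): 10 / (10 + 4320) = 0.23%. With follow-up of 80 h to 64 h (72 ± 8 h) the range is 0.21% to 0.26%.
- L = 50 min (an assumption: six injections, five gaps of 10 min): 50 / (50 + 4320) = 1.1%. The range is 1.0% to 1.3%.

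About 99% of the window after the first dose therefore lies outside the definition for new drugs with complete dates. This is a share of time, not of medications.

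**Step 3: effect of one subject on a table percentage**

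If a subject's only use of a drug falls in the gap, that drug's percentage falls by 1/N:

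- N = 50 (protocol sample size): 1/50 = 2.0 points.
- N = 30 (the reduced number of evaluable subjects in SAP 2.2 and 2.3): 1/30 = 3.3 points.
- ≤40 kg column: the documents give no N. Assuming 5 to 15 subjects, 1/5 = 20.0 points to 1/15 = 6.7 points.

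**Step 4: does any other section close the gap?**

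- Protocol 12.4.3 sets no time window for the medication summary. It does not conflict with SAP 6.1.3, but it does not correct it either.
- SAP Section 5 says missing or partial medication dates may be imputed, but its listed rules concern adverse events. Complete dates are untouched.
- SAP Section 9 declares one change for medications, the ATC level, and not the last-dose limit.
- SAP Section 1 gives the SAP precedence on planned analyses, so a programmer would follow 6.1.3.

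**The case against.** The strongest reply is that little is lost.

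- **The data remain visible.** Protocol 12.1 commits to listing all CRF data by subject, and SAP Section 5 says data for all enrolled participants go into the listings. Listing 16.2.4.3 is titled "Prior and Concomitant Medications", and nothing applies the last-dose limit to it. With 30 to 50 children it can be read line by line.
- **A treated reaction is reported elsewhere.** Protocol 10.3.7 and 12.4.5 require events that led to significant additional therapy to be reported and discussed as other significant adverse events.
- **The end-date sentence can be read more narrowly.** It may be meant only to separate drugs stopped before dosing from drugs continued through it. On that reading an incompletely dated drug started after the last injection is not tabulated either.
- **The percentages are only 1/N.** The 30 counts evaluable subjects, while Table 14.1.4.2 uses the Safety population, which may be larger.
- **Limiting concomitant use to the dosing period is a choice.** The protocol does not forbid it.

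The first two points stand and limit the consequence to the medication tables. The third also has some force: the literal text gives the asymmetry, but the intent is not stated. The narrower reading removes the asymmetry only by widening the gap. The fourth is right, and the figures in Step 3 are illustrations. The fifth does not rescue the rule. The plan collects medications for 72 hours, uses the word concomitant for what the follow-up calls record, and provides no other table for them.

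**Conclusion.** The definition is wrong as written. A fully dated medication started after the last injection is in neither planned table, and no other section restores it. The size is modest: 2.0 to 3.3 percentage points per affected subject and drug at N = 50 to 30, and more in a small weight-group column. The number of affected subjects cannot be estimated, because the documents give no medication rate.

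The conclusion assumes that start times, not only dates, are compared with the last injection. The SAP does not say which. If only dates are compared, a start on the dosing day could count as concomitant, and the gap would cover starts on later days up to 72 hours, which is the period the two calls document. The gap exists either way.

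No efficacy endpoint, adverse event count, vital-sign or ECG summary, or dose conclusion is affected. It should be corrected, but it is not critical.

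**What to change.** In SAP 6.1.3, replace the last-dose limit on newly started drugs with the end of the 72 ± 8 hour follow-up. Flag drugs started after the last injection in Table 14.1.4.2 and Listing 16.2.4.3, so that use during and after the injection session can be told apart. State in the same paragraph whether the comparison uses date and time or date alone. A separate post-treatment category with its own table would also close the gap, at the price of one more output.

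The cost is one SAP sentence with that clarification, one derivation and one flag. The data are already collected.

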6.2 Subject Disposition

The number of subjects for each of the following categories will be summarized, overall and by weight group (≤ 40 , > 40 kg):

- Enrolled subjects
- Subjects who received at least one dose of study drug (i.e., the safety population).
- Subjects included in the FAS population
- Subject included in the PP population
- Subjects who completed the study
- Subjects who withdrawn from the study and the reason for withdrawal

All protocol deviations will be listed. Deviations will be classified as Important or Non-important. Important deviations excluding from the PP population will be identified.

6.3 Study Drug Exposure and Compliance

The total treatment exposure (OPTISON injection in mL as well as number of administrations) received at two dose levels will be summarized by descriptive statistics overall and by weight group (≤ 40 , > 40 kg) based on Safety population. A summary of each subject's dosing information will be presented in a listing. The injection used for image interpretation will be identified in this listing. Reasons why OPTISON dose was repeated will also be listed.

6.4 Efficacy Analysis

6.4.1 General Considerations

Since this is a dose-finding study, no hypotheses are being tested. All efficacy results will be summarized for the FAS and PP populations.

Assessments to be used for image interpretation are identified by the site and recorded in the eCRF. These identified assessments will be used for efficacy analyses.

Efficacy summaries will be presented for each reader.

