8.1 Investigational Medicinal Product

8.1.1 OPTISON

OPTISON (Perflutren Protein-Type A Microspheres Injectable Suspension, [USP]) is a sterile non-pyrogenic suspension of perflutren-containing microspheres (5.0 to 8.0×10^8 /mL with a mean diameter range of 3.0 to 4.5 μm) of heat-treated human serum albumin with perflutren for contrast enhancement during the indicated ultrasound imaging procedures. The approximate amount of perflutren gas in each milliliter of OPTISON is 0.19 mg corresponding to 7 μL . The vial contains a clear liquid lower layer and a white upper layer that, after resuspension by gentle mixing, provides a homogeneous, opaque, milky-white suspension for intravenous injection. OPTISON will be provided in 3-mL vials for single use. OPTISON should be stored refrigerated at 2°C to 8°C (36°F to 46°F). Investigators must follow the package insert instruction to prepare and administer OPTISON.

In adults, the recommended dose of OPTISON ranges from 0.5 to 3.0 mL injected into a peripheral vein with the maximum total dose not exceeding 8.7 mL in any one patient. However, there is no established dosage for children. For this study, the dose information is based on 2 publications using OPTISON in pediatric echocardiography (see Section 6.2.1). Each patient will receive 2 different doses of OPTISON administration for CE-ECHO; the actual doses of OPTISON will be based on pediatric body weight of ≥ 20 to ≤ 28 kg, > 28 to ≤ 40 kg, and > 40 kg and up to 3 injections per dose level are allowed for acquiring different imaging views (Table 1). According to the low volume of OPTISON required for these children, the volume of OPTISON will be diluted within the same volume of saline to facilitate the injection.

Table 1 OPTISON Dosing Table

Body weight (kg)	Dose/injection (mL) Dose level 1	Dose/injection (mL) Dose level 2	Total dose (mL) not to exceed (3 injections/dose level)
≥ 20 to ≤ 28	0.1	0.2	1.0
> 28 to ≤ 40	0.2	0.3	1.5
> 40	0.2	0.4	1.8

The contrast will be administered as a slow bolus at a steady rate of approximately 0.05 mL per second for contrast-enhanced echocardiographic imaging followed by a 5.0 mL slow injection of saline. Injections should be at least 10 minutes apart to allow for clearance of the previous dose.

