2.2 Study Design

This is a Phase 4, open-label, non-randomized, multi-center, multi-dose study in North America and Europe. The study is designed to evaluate overall efficacy and safety of intravenous administration of OPTISON at various doses in pediatric patients undergoing transthoracic echocardiography.

Approximately 50 pediatric patients between ≥ 9 and <18 years of age weighing ≥ 20 kg who are clinically indicated for a transthoracic echocardiogram and are likely to have a limited transthoracic echocardiographic window based on body habitus and/or previous cardiac operation or have a previous suboptimal non-contrast echo cardiogram will be enrolled into the study. Per FDA Advice/information request dated 2023, February 16th, a reduction of the sample size to 30 evaluable subjects was agreed.

OPTISON will be administered according to pediatric body weight (≥ 20 to ≤ 28 kg, >28 to ≤ 40 kg, and >40 kg). Each patient will receive administrations of 2 different dose levels. Up to 3 injections per dose level are allowed to be administered if significant technical issue(s) have occurred e.g., patient related needs, scanner malfunction, or drug injection error, with the total injected dose not to exceed the value defined in Table 1. Injections should be at least 10 minutes apart between the 2 dose levels to allow for clearance of the previous dose.

Table 1 OPTISON Dosing Table

Body weight (kg)	Dose/injection (mL) Dose level 1	Dose/injection (mL) Dose level 2	Total dose (mL) not to exceed (3 injections/dose level)
≥ 20 to ≤ 28	0.1	0.2	1.0
>28 to ≤ 40	0.2	0.3	1.5
>40	0.2	0.4	1.8

[figure not shown]
For echocardiographic imaging, standard apical 4-chamber and 2-chamber views will be obtained at baseline using tissue harmonic imaging, thereafter with contrast using a contrast-imaging mode. Additional views may be obtained at the clinician's discretion. All image views will be obtained prior to and after contrast administration until 10 minutes post injection. All images will be recorded on disk and sent to sponsor's image core lab for preparation of blinded image evaluation (BIE).

Efficacy of echocardiographic images will be evaluated by independent blinded readers based on characteristics of left ventricular opacification (LVO), diagnostic confidence of LV EBD and wall motion, and diagnostic confidence of LVEF. Echocardiographic Analyses as per independent review charter includes:

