2.5 Randomization and Blinding

This is an open-label study. No blinding will be conducted for the subject allocation or application of the investigational medicinal product (IMP) in this study.

For determination of efficacy and optimal dose level, 3 qualified independent blinded readers will conduct BIE of echocardiographic images. Non-contrast and OPTISON-

enhanced images will be presented in random order to the 3 readers without dosing information.

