- All mean and median values, as well as Q1 and Q3, will be formatted to one more decimal place than the measured value. Standard deviation values will be formatted to two more decimal places than the measured value. Minimum and maximum values will be presented with the same number of decimal places as the measured value.
- All p-values, if applicable, will be rounded to 4 decimal places. All p-values that round to 0.0000 will be presented as ‘<0.0001’ and p-values that round to 1.0000 will be presented as ‘>0.9999’. Two-sided P-values < 0.05 will be considered to be statistically significant unless otherwise specified.
- All summary tables will include the analysis population sample size (*i.e.*, number of subjects).

- Study Day 1 is defined as the date at which the subject receives the first dose of study medication. All study days are determined relative to Day 1.
- Study days prior to Day 1 will be calculated as:
 - Study Day = Assessment Date – First Injection Date
- Study days after Day 1 will be calculated as:
 - Study Day = Assessment Date – First Injection Date + 1.
- Baseline values will be defined as the last non-missing value recorded prior to first dose of study drug.
- Change from baseline will be calculated as follows: Change = Post-baseline value - baseline value.
- All pre- and post- investigational product assessments including unscheduled or repeat assessments will be included in the data listings. For unscheduled or repeat pre-dose assessments, the last assessment taken for a time point will be used in the data summaries (summary tables, figures, and statistical analysis); for all post-dose time points, the initial assessment for any given time point will be used in the safety data summaries (summary tables, figures, and statistical analysis, except the summary tables of clinically notable values and shift tables where all values will be included). For efficacy summaries, the site records in the eCRF which assessment was considered for the image interpretation. The corresponding assessment will be used in the efficacy summaries.
- Date variables will be formatted as DDMMYY for presentation.
- Tables, figures, and listings will be presented in landscape orientation.
- SAS® Version 9.4 or higher will be the statistical software package used for all data analyses.

Definition of Analysis Windows

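### The unblinded site identifies which acquisition feeds every efficacy analysis, and the SAP gives no rule for choosing when a dose level has more than one usable acquisition of the same view

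*SAP*

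**What the plan says.** SAP 6.4.1 gives the site the task of naming the assessment to be read ("Assessments to be used for image interpretation are identified by the site and recorded in the eCRF") and adds: "These identified assessments will be used for efficacy analyses". SAP 5 repeats the convention: "For efficacy summaries, the site records in the eCRF which assessment was considered for the image interpretation". The same bullet in SAP 5 does set a rule for most post-dose safety summaries, namely the initial assessment at each time point. Efficacy has no equivalent.

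The documents differ on why a dose level may have several injections. SAP 2.2: "Up to 3 injections per dose level are allowed to be administered if significant technical issue(s) have occurred"; its examples include patient needs as well as scanner and injection faults. Protocol 8.1.1: "up to 3 injections per dose level are allowed for acquiring different imaging views", with no technical condition. Protocol 10.2.4 sends all echocardiographic images to the three readers. The SAP's summary of changes (section 9) does not mention site selection.

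On blinding, SAP 2.5 says of the study itself: "No blinding will be conducted for the subject allocation or application of the investigational medicinal product (IMP) in this study". Of the reading it says: "3 qualified independent blinded readers will conduct BIE of echocardiographic images", without dosing information.

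SAP 6.3 summarises the number of administrations at the two dose levels, lists the injection used for interpretation, and lists the reasons for repeats.

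**The concern.** The person who identifies the acquisition knows the dose and can see the images. If two usable acquisitions of the same view exist at one dose level, nothing in either document stops the better-looking one from being put forward. Blinded reading cannot undo a selection made before it.

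The choice reaches the primary segment count with its confidence interval and paired t-tests (SAP 6.4.2). It also reaches opacification, duration and the subject-level suitability composite (SAP 6.4.3). Repeats may be more frequent at one dose level than the other, so the comparison of doses is exposed as well.

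It can also bypass the plan's own protections. The FAS keeps children whatever the quality of their contrast images, uninterpretable images score zero (SAP 6.4.4), and weak enhancement is not a protocol deviation (SAP 9). Poor contrast results are meant to count. A poor acquisition that is passed over never meets those rules.

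**Working it through.** The plan states no figure for the effect of selection, so there is none to reproduce. The check asks whether several candidates can exist, and how large the effect could be.

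**Step 1. Can three candidates per level exist?** Doses and caps are from Table 1 of Protocol 8.1.1 and SAP 2.2. Three injections at both levels total:
- 20 to 28 kg: 3 × (0.1 + 0.2) = 0.9 mL, cap 1.0 mL
- over 28 to 40 kg: 3 × (0.2 + 0.3) = 1.5 mL, cap 1.5 mL
- over 40 kg: 3 × (0.2 + 0.4) = 1.8 mL, cap 1.8 mL

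The documents' own limits therefore allow three per level in every weight group.

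**Step 2. Worst-case shift per repeated child.** Take k independent, equally distributed normal repeats with within-child SD σ, and suppose the best is always chosen. The expected gain is c(k) × σ, with c(2) = 1/√π = 0.564 and c(3) = 3/(2√π) = 0.846. A simulation of 2,000,000 draws gave 0.565 and 0.847. The documents give no σ. With an assumed 1 to 2 segments, the gain is 0.56 to 1.13 segments for best of 2 and 0.85 to 1.69 for best of 3.

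**Step 3. Worst-case shift in the mean.** Shift = f × c(k) × σ, where f is the share of children with a repeat. The documents do not give f, so a range is shown.

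| f (assumed) | Lowest: best of 2, σ = 1 | Highest: best of 3, σ = 2 |
|---|---|---|
| 10% | 0.10 × 0.564 × 1 = 0.06 | 0.10 × 0.846 × 2 = 0.17 |
| 20% | 0.20 × 0.564 × 1 = 0.11 | 0.20 × 0.846 × 2 = 0.34 |
| 30% | 0.30 × 0.564 × 1 = 0.17 | 0.30 × 0.846 × 2 = 0.51 |

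**Step 4. Paired t-test.** Simulation with 30 children (the evaluable number in SAP 2.3), no true contrast effect, best of 3 in a share f, a single comparator acquisition, and 20,000 trials per setting. The two-sided rate of p < 0.05 was 4.8% at f = 0 and about 6%, 10% and 16% at f = 10%, 20% and 30%.

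**Step 5. Suitability composite.** If one injection meets all four criteria with probability p (assumed), at least one of three independent injections does with probability 1 − (1 − p)³: 0.66, 0.88 and 0.97 for p = 0.3, 0.5 and 0.7. With p = 0.5 and f = 20%, the reported percentage moves from 50% to 0.5 + 0.2 × (0.875 − 0.5) = 57.5%.

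**The case against.** A reader might infer that contrast gets a free best-of-three pick in every child while the non-contrast comparator gets a single attempt. The documents do not support that.

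- SAP 2.2 ties repeats to significant technical issues. A repeat then often replaces a failed acquisition and leaves no real choice.
- Under Protocol 8.1.1 the injections may serve different views. The 12 segments need both the 4-chamber and 2-chamber views, so such injections are complementary parts of one assessment.
- SAP 5 and 6.4.1 do not restrict site identification to contrast images. Only one baseline non-contrast acquisition is described, but Protocol 10.2.2 allows additional views before as well as after contrast.
- Segment counts are whole numbers from 0 to 12, the site judges by eye, and three independent readers give the scores. The gains in Steps 2 to 5 assume a site that always picks the acquisition later scored highest.
- SAP 6.3 makes the choice visible and allows reanalysis, and SAP 6.4.1 says no hypotheses are tested.
- Reading and acquisition details are deferred to the Independent Review Charter and the Imaging Manual, which are not among the documents reviewed. A rule may exist there.

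All of this stands, and it reduces the likely size. It does not supply the missing rule. The technical condition is loosened by the patient-needs example and is absent from the protocol. SAP 1 gives the SAP precedence on planned analyses only, so it does not clearly override the protocol on how injections are given. Even after a technical issue, nothing says which acquisition counts. Listing the choice neither prevents selection nor measures its effect. The paired t-tests are still reported, with a 0.05 threshold in SAP 5.

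**Conclusion.** The concern holds in a limited form. For children with more than one usable acquisition of the same view at a dose level, an unblinded site decides which enters all efficacy analyses, and neither document gives a selection rule or a sensitivity analysis.

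The worst case is 0.56 or 0.85 within-child SD per repeated child. At an assumed 20% repeat share and an SD of 1 to 2 segments this is about 0.1 to 0.3 of 12 segments on the mean, and it scales in proportion to the repeat share. The t-test and suitability figures are bounds of the same kind. They rest on assumed repeat shares and probabilities, on independent repeats and, for the t-test, on a single comparator acquisition. They are not forecasts.

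Because the efficacy aim is descriptive, the main harm is inflated estimates and suitability percentages. The documents show that selection is possible. They do not show that it is systematic or that it favours contrast only.

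**What to change.** Replace the site's choice in SAP 5 and 6.4.1 with a prespecified rule. For each view and each condition (non-contrast, dose level 1, dose level 2), analyse the first acquisition that has no technical failure recorded in the eCRF before image review. The core lab, which already receives all images, should apply the rule without dose information. If the charter already contains a rule, the SAP should state it.

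The rule has to work per view: analysing only the first injection could drop up to half of the 12 segments when views come from separate injections.

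Add one sensitivity analysis, either limited to children with no repeat of the same view, or using the first acquisition per view with documented injection or scanner failures excluded. Using the first injection regardless would not serve, because uninterpretable images from such failures would score zero under SAP 6.4.4 and would measure mishaps, not dose.

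Tabulate repeats and their reasons by dose level. This also keeps the remaining site discretion, the recording of a technical failure, open to inspection. Reconcile Protocol 8.1.1 with SAP 2.2 on when repeats are allowed, and Protocol 10.2.4 with SAP 6.4.1 on which images are read; declare any change in SAP 9.

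The cost is SAP and charter wording, a little extra core-lab work, and a few children analysed on a less favourable image.
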